22.5 Adverse Events of Special Interest

AEs of special interest for this study are outlined below. Adverse events of special interest will be followed until resolution or return to baseline.

- Elevated blood pressure (defined as systolic blood pressure ≥ 180 and diastolic blood pressure ≥ 100 mm Hg).
- Hyperglycemia (HbA1c $> 6.5\%$, or fasting plasma glucose > 126 mg/dL, or classic symptoms of hyperglycemia with random plasma glucose > 200 mg/dL).
- MedDRA System Organ Class infection/infestation that are considered SAEs or lead to treatment discontinuation.
- Hy's Law cases (ALT $> 3 \times$ ULN, with total bilirubin $> 2 \times$ ULN, no initial signs of cholestasis [alkaline phosphatase within the reference range], and no other reason can be found to explain liver injury).

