19.6 Vital Signs

Vital signs will be obtained after the subject has been seated for 5 minutes (minimum) and will include systolic and diastolic blood pressures, pulse rate, respiratory rate, and body temperature. Additionally, at the Screening and Randomization Visits, blood pressure will be measured 3 times, with at least 5 minutes between assessments after the subject has been seated for a minimum of 5 minutes prior to the initial blood pressure assessment.

The investigator may perform additional unscheduled vital sign measurements to evaluate or manage a suspected AE. These unscheduled vital sign measurements should be obtained after the subject has been seated for at least 5 minutes, if possible. Unscheduled vital signs will be recorded.

The date and time for all vital sign assessments will be recorded.

Screening/Randomization

A subject with systolic blood pressure > 150 mm Hg and diastolic blood pressure > 90 mm Hg (average of 3 assessments) at the Screening or Randomization Visits does not qualify for the study.

On Study Assessments

If an on-study systolic blood pressure is > 150 mm Hg and diastolic blood pressure is > 90 mm Hg, an AE will be recorded if the investigator determines the change is clinically significant or requires a change in the subject's clinical management.

19.7 Clinical Laboratory Tests (Chemistry, Hematology and Urinalysis), HbA1c, IGRA, Direct Coombs test, Pregnancy Tests, ■■■■ ■■■■; and C3, C4, and anti-ds DNA antibodies

The clinical laboratory tests are listed in Attachment 1. All clinical laboratory tests will be done at a central laboratory facility except urine pregnancy (at the site) and ■■■■
■■■■. Specific instructions for collection, processing, storage, and shipment of clinical laboratory samples will be provided in a separate laboratory manual, where appropriate.

Samples for laboratory testing at all visits may be collected under fasted or nonfasted conditions. Fasting early morning samples are preferred, but a random daytime sample is acceptable. The date and time of the sample collection must be documented on the laboratory report. Investigators must review and sign laboratory reports. The clinical significance of each laboratory abnormality will be documented. New clinically significant laboratory abnormalities or clinically significant changes in laboratory values will be reported as AEs.

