Hematology with differential, serum chemistry, and urinalysis samples will be collected at the specific times starting at screening and throughout the study.

In addition:

- All female subjects of child-bearing potential will have a serum pregnancy test at the Screening and Follow-up Visits. A positive urine test after randomization will be confirmed by a serum pregnancy test. Urine pregnancy tests will be done at other specified visits throughout the study. Results must be available prior to dosing with protocol mandated study drug. Subjects with positive results will be ineligible for study entry (Screening Visit or Randomization) or withdrawn from the study. Any

female subject that becomes pregnant during the study will be immediately withdrawn and the pregnancy reported as per [Section 21.6](#).

If applicable, the subject's agreement to use contraception throughout their study participation, and for 28 days after ending study participation, will be documented.

- A lipid panel (high density lipoprotein, low density lipoprotein, triglycerides, and total cholesterol) will be done at the Screening, Randomization, Week 12, and Week 24 Visits.
- HBsAg and HBcAb will be performed at the Screening Visit. Results of these tests must be negative or nonreactive for subjects to qualify for the study.
- HCV will be performed at the Screening Visit. A positive HCV will automatically trigger a HCV PCR analysis. HCV PCR must be < 25 IU/mL to qualify for the study.
- IGRA for TB will be performed at the Screening Visit. Results of this test must be negative for subjects to qualify for the study.
- HbA1c will be performed at the Screening Visit. HbA1c must be $\leq 6.5\%$ for subjects to qualify for the study. Additional HbA1c tests will be done at specified times during the protocol.

■ [REDACTED]
[REDACTED]

- C3, C4, and anti-ds DNA antibody samples will be taken at specified times during the study. -

Out-of-Range Laboratory Values

Laboratory values from samples collected at the Screening Visit will be evaluated by the investigator for eligibility of the subject in the study. Clinical laboratory tests may be repeated once to determine subject eligibility.

Laboratory values that fall outside the reference range from samples collected at the Randomization Visit and throughout the study will be assessed by the investigator for clinical significance. If the out of range value is deemed clinically significant by the investigator, an AE will be recorded.

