22.4 Adverse Event and Serious Adverse Event Recording and Reporting

AEs and SAEs will be recorded from signing of the ICF through completion of the Follow-up Visit. The investigator is required to record the AE or SAE regardless of the severity of the event or its relationship to study treatment. The investigator must follow up on all AEs and SAEs reported to have occurred through the Follow-up Visit until the event has resolved or stabilized or at such time the investigator refers the subject to a nonstudy physician. The investigator will document the further follow-up information in the subject's source document.

During the period specified above, the investigator will:

- Record all AEs and SAEs from the signing of the ICF through the completion of the Follow-up Visit.
- Report all SAEs on an SAE Report Form to Global Pharmacovigilance.
- Report all pregnancies to Global Pharmacovigilance on the Pregnancy Surveillance Form.
- Submit any Expedited Safety Report or Suspected Unexpected Serious Adverse Reaction from Global Pharmacovigilance to the IRB/IEC.

The reporting requirements for AEs are summarized in Table 22-3.

Table 22-3: Reporting Requirements for Adverse Events

Seriousness	Reporting Time	Type of Report
All Serious	Within 24 hours of first knowledge of event	Initial report on the SAE Form, appropriate eCRF, and source document
	Within 24 hours of receipt of follow-up information	Follow up report on the SAE Form, appropriate eCRF, and source document
Nonserious	Per case report form submission procedure	Appropriate eCRF and source document

Adverse Events

Adverse events can be reported spontaneously or elicited during open-ended questioning (ie, "How have you been feeling since your last visit?"), examination, or evaluation of a subject. Signs and symptoms must be recorded using standard medical terminology. For subjects incapable of giving consent, the legally acceptable representative may provide information regarding the subject's status.

All fields on the AE CRF page should be completed for each event with a full description of the event and date of onset/start and resolution/stop. A medical diagnosis if known, should be recorded in lieu of each individual sign and symptom associated with the diagnosis and experienced by the subject. If no medical diagnosis is known, the term used by the subject to describe the event or signs noted by the site personnel should be recorded.

Serious Adverse Events

Initial Reporting

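### Section 22.5 sets blood pressure and glycemic events of special interest by fixed limits, but 19.6 and 19.7 leave their recording as AEs to the investigator, and the visible analysis does not count subjects who meet the limits

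*Combined protocol and SAP*

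**What the plan says.** Section 22.5 lists four adverse events of special interest (AESIs):

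- Elevated blood pressure: "systolic blood pressure ≥ 180 and diastolic blood pressure ≥ 100 mm Hg".
- Hyperglycemia: HbA1c above 6.5%, "or fasting plasma glucose > 126 mg/dL, or classic symptoms of hyperglycemia with random plasma glucose > 200 mg/dL".
- Infections: "MedDRA System Organ Class infection/infestation that are considered SAEs or lead to treatment discontinuation".
- Hy's Law: limits on ALT, total bilirubin and alkaline phosphatase, with the added condition that "no other reason can be found to explain liver injury".

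The only instruction attached to the list concerns follow-up: "Adverse events of special interest will be followed until resolution or return to baseline".

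The rules that turn a measurement into an AE are in Section 19. For laboratory values, 19.7 says: "If the out of range value is deemed clinically significant by the investigator, an AE will be recorded". For on-study blood pressure above 150 systolic and 90 diastolic, 19.6 says that "an AE will be recorded if the investigator determines the change is clinically significant", and the sentence goes on to allow a second route, a required change in the subject's clinical management.

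Table 22-3 has two reporting classes. Serious events go within 24 hours. Nonserious events go "Per case report form submission procedure". AESIs have no row of their own.

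**The concern.** An AESI list with fixed limits exists so that the same finding is counted in the same way at every site. Here the limits define the event, but the gate to the AE record is individual judgment at about 60 sites. Section 10.5 names altered glucose tolerance and raised blood pressure among the common reactions to the drug, so these harms are expected.

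Two things are at stake. A subject with a qualifying value but no AE record does not enter the AESI follow-up, which is stricter than the ordinary rule in 22.4 (follow-up there may end at stabilization or on referral to a nonstudy physician). And an AESI rate built from AE records would reflect how often investigators chose to record as well as how often the limits were crossed.

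**Working it through.** No figure in the plan bears on this point, so the check sets the passages side by side.

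**1. Which AESIs are purely numeric?**

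| AESI in 22.5 | Numeric alone? |
|---|---|
| Blood pressure | Yes, a paired systolic and diastolic limit |
| Hyperglycemia, HbA1c route | Yes |
| Hyperglycemia, fasting glucose route | Yes, but only if the sample was fasting |
| Hyperglycemia, random glucose route | No, symptoms are also needed |
| Infections | No, set by seriousness or treatment discontinuation |
| Hy's Law | In part: laboratory limits plus exclusion of other causes |

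**2. Do the limits differ between sections?** For blood pressure they are nested. Any reading of at least 180 and at least 100 is also above 150 and above 90, so every reading that meets 22.5 falls under the 19.6 rule. The gap is therefore the investigator's determination and not a mismatch of thresholds.

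**3. A worked case (hypothetical values).** A subject enters with HbA1c 6.4%, which is eligible because 19.7 requires no more than 6.5%. At Week 12, one of the two scheduled on-treatment HbA1c times, the value is 6.7%. Since 6.7 > 6.5, the 22.5 limit is met. Under 19.7 it becomes an AE only if the investigator deems it clinically significant. If not, there is no AE record.

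**4. Passages pointing the other way.** Section 16.3.1 uses the same blood pressure and glycemic limits among its reasons to stop study drug (where concomitant medication cannot manage the condition). Its last item refers to any *other* adverse event, which implies that the items before it are AEs. Section 23.1 likewise speaks of the adverse events described in that list, although its cross-reference is to 15.3.1. Section 22.5 itself introduces its list as AEs. No sentence says which rule governs.

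**5. Does the visible analysis recover the count?**

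- AEs (21.8) are summarized from recorded events by body system, preferred term, severity and causality.
- Vital signs are summarized at each visit. Separate systolic and diastolic summaries do not give the number of subjects with a paired reading at or above both limits.
- Laboratory results are listed by subject and summarized by visit, with shift tables if applicable. Abnormal values are to be analyzed, but neither the 22.5 limits nor the combined liver criterion is named.
- HbA1c (21.8.5) is listed and summarized descriptively or graphically.
- The safety endpoints in 21.4 do not mention AESIs.

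**6. Size.** Let *p* be the true proportion of an arm meeting a limit and *q* the fraction of those recorded as AEs. The expected recorded proportion is *q* × *p*, and the expected difference between arms is *q*(A)*p*(A) − *q*(P)*p*(P). With the same *q* in both arms this is *q* times the true difference. If *q* differs between arms, the distortion can go either way. The documents give neither *p* nor *q*, so *q* can be anything from 0 to 1 and no numerical loss can be stated.

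**The case against.** The strongest reply is that 22.5, read with 16.3.1 and 23.1, already makes these values AEs by definition, so the HbA1c case above would be recorded. That reading is reasonable. But 19.6 and 19.7 are the explicit recording rules and contain no exception for it. The objection therefore shows a conflict and does not remove one.

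It is also fair to say that absence is not proven. The text of Section 19.1 is not visible, parts of Section 21 are redacted, and the SAP to which Section 21.6 refers is a separate document. A recording rule or an AESI table could be in any of them. This limits the point about the missing count in particular.

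A reader might infer more than the documents support, in four ways:

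- *That evidence of harm is lost.* It is not. Laboratory values are listed and summarized whether or not they are AEs, and vital signs are summarized at each visit. What may be incomplete is the event count and the special-interest follow-up.
- *That every AESI is an objective limit overridden by opinion.* Infections have no numeric limit, Hy's Law needs a causal judgment, and one hyperglycemia route needs symptoms. For blood pressure, a required change in management is a second route to an AE.
- *That AESIs reach the sponsor late.* This could apply only to nonserious ones. Serious infections go within 24 hours, and 22.4 has doubtful cases treated as serious. Chemistry is run centrally, laboratory data are processed electronically, and the medical monitor reviews the data (27.2). No review frequency is given, so neither delay nor promptness can be shown.
- *That a stated amount of statistical power is lost.* AEs are summarized descriptively, no test of AESI rates is planned in the visible text, and any crossing rates would be invented.

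**Conclusion.** The point holds in limited form. For the paired blood pressure limit, HbA1c and fasting glucose, the definition in 22.5 and the recording rules in 19.6 and 19.7 do not agree, and 16.3.1 and 23.1 lean toward 22.5. Applied literally, Section 19 allows a qualifying value to have no AE record and no AESI follow-up. The visible analysis does not count subjects meeting the limits, nor those meeting the combined liver criterion.

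The consequence is confined to the safety tabulation and follow-up; the primary efficacy analysis is untouched. Its size cannot be estimated from the documents. The conclusion assumes that neither the text not visible nor the separate SAP contains an overriding recording rule or an AESI derivation. If the SAP has such a derivation, only the conflict over recording remains.

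**What to change.** 1. **Reconcile the recording rule.** State in 22.5, with cross-references in 19.6 and 19.7, that a value meeting a purely numeric 22.5 limit is recorded as an AESI regardless of the clinical-significance judgment. Values meeting the ALT, bilirubin and alkaline phosphatase part of the Hy's Law criterion should be recorded as potential cases pending causality assessment. Symptomatic hyperglycemia and infections stay as defined, since they cannot be decided from a number. Align the wording of 16.3.1 and 23.1 on whether the listed conditions are AEs, and correct the 23.1 cross-reference.

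2. **Count from the data.** For the Safety Population, tabulate by arm the subjects meeting each numeric limit: paired blood pressure, HbA1c, glucose only where fasting status is known (19.7 allows nonfasting samples), and the combined liver criterion. Derive these from the vital-sign and central-laboratory data and show them alongside recorded AESIs, with risk difference and 95% CI. The gap between the two columns then shows how complete recording was.

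3. **Reporting time.** The sponsor should state in Table 22-3 which timetable applies to nonserious AESIs. The documents do not determine what it should be.

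The cost is protocol and SAP wording, one derived table and some additional AE records. No new assessment is needed.

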8.2 Schedule of Study Events

Table 8-1: Schedule of Study Events

Assessment/Procedure	Screening (Day-28 to Day -1)	Randomization	Dosing	Treatment Period								Follow-up
Week		0	0	2 (± 3 days)	4 (± 3 days)	6 (± 3 days)	8 (± 3 days)	12 (± 5 days)	16 (± 5 days)	20 (± 5 days)	24 (± 5 days)/Early Termination	28 (± 5 days)
Informed Consent	X											
Inclusion/Exclusion Criteria Review	X	X										
Demographics	X											
Medical/Surgical History	X											
Current Medical Condition Review		X		X	X	X	X	X	X	X	X	X
Complete Physical Examination	X										X	
Limited Physical Examination		X		X	X	X	X	X	X	X		X
Height and Weight ^a	X	X		X	X	X	X	X	X	X	X	X
Vital Signs ^b	X	X		X	X	X	X	X	X	X	X	X
12-lead ECG	X										X	
Clinical Laboratory Tests ^c	X	X		X	X	X	X	X	X	X	X	X
Lipid Panel	X	X						X			X	
HbA1c	X							X			X	
Serum Pregnancy Test	X										X	
Urine Pregnancy Test ^d		X					X		X			X
IGRA for TB	X											
Hepatitis Serology ^c	X											
		X						X			X	
C3, C4 and anti-ds DNA antibodies	X	X		X	X	X	X	X	X	X	X	
Serology (ANA, ENA) ^f	X											

Assessment/Procedure	Screening (Day-28 to Day -1)	Randomization	Dosing	Treatment Period								Follow-up
Week		0	0	2 (± 3 days)	4 (± 3 days)	6 (± 3 days)	8 (± 3 days)	12 (± 5 days)	16 (± 5 days)	20 (± 5 days)	24 (± 5 days)/Early Termination	28 (± 5 days)
		X					X		X		X	
		X					X		X		X	
		X					X		X		X	
SLEDAI-2K	X	X		X	X	X	X	X	X	X	X	
BILAG-2004	X	X			X		X	X	X	X	X	
PGA		X			X		X	X	X	X	X	
SFI					X		X	X	X	X	X	
CLASI-Activity		X			X		X	X	X	X	X	
28 Joint Count		X			X		X	X	X	X	X	
		X					X		X		X	
		X					X		X		X	
Hospital Admissions				X	X	X	X	X	X	X	X	
IXRS Contact	X	X		X	X	X	X	X	X	X	X	
Study Drug and Diary Training		X										
Study Drug Accountability and Diary Review				X	X	X	X	X	X	X	X	
Dispense Study Drug and Diary		X		X	X	X	X	X	X	X		
Administer First Dose			X									
Adverse Events and Concomitant Treatments								X				

^aHeight at screening only.

^bBlood pressure, respiratory rate, pulse rate and body temperature. For blood pressure, an average of 3 readings after the subject has been seated for ≥ 5 minutes at The Screening and Randomization Visits. Single readings after subject has been seated for ≥ 5 minutes at all other time points.

^cChemistry, hematology assays, and urinalysis (see Attachment 1).

^dPositive urine test after randomization will be confirmed by serum pregnancy test.

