16.3.1 Treatment Discontinuation

Treatment with study drug should be discontinued if any of the following occur:

- Development of accelerated hypertension (defined as systolic blood pressure ≥ 180 and diastolic blood pressure ≥ 100 mm Hg) that cannot be managed by the adjustment of concomitant medications such as antihypertensive medications.
- Development of congestive heart failure (Class III or IV) that cannot be managed by the adjustment of concomitant medications such as diuretics and antihypertensive medications.
- Development of diabetic signs/symptoms (ie, HbA1c > 6.5 , or fasting plasma glucose > 126 mg/dL, or classic symptoms of hyperglycemia with random plasma glucose > 200 mg/dL) that cannot be managed by the adjustment of concomitant medications such as insulin and oral hypoglycemic agents.
- Development of any other adverse event (AE) of at least moderate intensity and possibly, probably or definitely related to study drug that cannot be managed by the adjustment of concomitant medications.

Missed doses of study drug should be discussed with the medical monitor.

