19.3 Current Medical Conditions

At each visit after screening, subjects will be asked about any changes in medical conditions, specifically new medical conditions and worsening of existing medical conditions. Any changes since the Screening Visit will be recorded as AEs, as appropriate.

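### The on-study AE prompt for blood pressure (19.6) and the blood-pressure AESI (22.5) each require both limits, so an isolated severe rise such as 210/88 triggers neither and gets only ordinary AE handling

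*Combined protocol and SAP*

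**What the plan says.** **AESI (22.5).** The listed event is "Elevated blood pressure (defined as systolic blood pressure ≥ 180 and diastolic blood pressure ≥ 100 mm Hg". Its follow-up is stricter than for other events: "Adverse events of special interest will be followed until resolution or return to baseline".

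**Ordinary AEs and SAEs (22.4).** These are followed "until the event has resolved or stabilized or at such time the investigator refers the subject to a nonstudy physician".

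**On-study prompt (19.6).** "If an on-study systolic blood pressure is > 150 mm Hg and diastolic blood pressure is > 90 mm Hg, an AE" is to be considered, and "an AE will be recorded if the investigator determines the change is clinically significant" or it calls for a change in management.

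**Stopping study drug (16.3.1).** The blood-pressure criterion is "Development of accelerated hypertension (defined as systolic blood pressure ≥ 180 and diastolic blood pressure ≥ 100 mm Hg", when it cannot be managed with other medication. This is the same pair of limits as the AESI.

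**Measurement (Table 8-1, footnote b).** Screening and Randomization use the average of three readings. After that: "Single readings after subject has been seated for ≥ 5 minutes at all other time points".

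**General capture (19.3).** Subjects are asked about new or worsening conditions at each visit after screening: "Any changes since the Screening Visit will be recorded as AEs, as appropriate".

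**The concern.** Section 10.5 names raised blood pressure among the common reactions to this drug, so the rules that bring it to attention matter. Both rules join their limits with the word and. A large rise in one pressure alone therefore reaches neither rule if the other pressure stays at or below its 19.6 limit. A subject who entered with mean systolic pressure of at most 150 could reach 210/88, at least 60 mm Hg above the entry ceiling, without meeting either.

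Two things are at stake. The first is prompting: nothing specific to blood pressure asks the investigator to judge such a reading. The second is closure: if it is recorded, the event may end at stabilization or referral, even with the pressure still high. Table 8-1 measures vital signs at every visit through Week 28 whatever the AE status. The closure difference therefore matters mainly for events that are unresolved at the Follow-up Visit or handed to a nonstudy physician.

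**Working it through.** **Step 1: apply the wording to example readings.**

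| Reading | 19.6 prompt (>150 and >90) | 22.5 AESI (≥180 and ≥100) |
|---|---|---|
| 210/88 | no (88 is not >90) | no (88 is not ≥100) |
| 148/115 | no (148 is not >150) | no (148 is not ≥180) |
| 210/95 | yes | no |
| 180/100 | yes | yes |

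The visible text contains no either-limit rule for on-study readings.

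**Step 2: compare with the entry criterion.** Inclusion criterion 10 caps each pressure separately, so 160/85 fails it. The screening sentence in 19.6 disqualifies only when both limits are exceeded, so 160/85 passes there. The on-study sentence repeats that joint form. This suggests that the joint wording in 19.6 is a slip. The same comparison says nothing about 22.5, which matches 16.3.1.

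**Step 3: illustrate the size.** The documents give no on-treatment distribution and no count to reproduce, so every distributional input is an assumption.

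- Readings: 162 subjects × 8 on-treatment visits (Weeks 2, 4, 6, 8, 12, 16, 20, 24) = 1,296, with no dropout. These are readings, not subjects.
- Systolic S and diastolic D are taken as bivariate normal with correlation r of 0.5 or 0.7. Means and SDs are 135/82 and 140/85 with SD 18/11, and 130/80 with SD 15/10. The two higher means are high for subjects who entered at or below 150 and 90.
- Joint probability: J(a,b) = 1 − Φ((a−μS)/σS) − Φ((b−μD)/σD) + Φ₂((a−μS)/σS, (b−μD)/σD; r).
- Systolic-only = P(S≥180) − J(180,100). Diastolic-only = P(D≥100) − J(180,100).
- Outside both rules = P(S≥180, D≤90) + P(D≥100, S≤150).
- Either-limit 19.6 = P(S>150) + P(D>90) − J(150,90).

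Worked case, 135/82 with r = 0.5: P(S≥180) = 1 − Φ(45/18) = 1 − Φ(2.5) = 0.0062, or 8.05 readings. The joint count is 3.2, so systolic-only is about 4.8.

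Expected counts per 1,296 readings:

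| Means; r | Joint AESI | Systolic-only ≥180 | Diastolic-only ≥100 (of which ≥110) | S≥180 and D≤90 | All outside both rules | 19.6 as written → either limit (added) |
|---|---|---|---|---|---|---|
| 135/82; 0.5 | 3.2 | 4.8 | 62.7 (6.3) | 1.8 | 29.1 | 127 → 438 (311) |
| 135/82; 0.7 | 5.4 | 2.6 | 60.5 (5.3) | 0.4 | 14.4 | 162 → 402 (240) |
| 140/85; 0.5 | 7.9 | 9.1 | 104.0 (12.7) | 2.9 | 41.5 | 209 → 586 (377) |
| 140/85; 0.7 | 12.2 | 4.8 | 99.7 (10.5) | 0.6 | 20.0 | 253 → 542 (289) |
| 130/80; 0.5 | 0.23 | 0.33 | 29.3 (1.7) | 0.1 | 16.8 | 54 → 270 (217) |
| 130/80; 0.7 | 0.42 | 0.13 | 29.1 (1.6) | 0.01 | 9.8 | 74 → 250 (175) |

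**Step 4: compare two ways of widening 22.5.**

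- *Systolic ≥180 alone added.* This brings in the systolic-only column, fewer than 10 readings in every scenario. The largest total is 7.9 + 9.1 = 17.0 readings.
- *Either limit, with diastolic ≥100 alone.* The total becomes 69 to 121 readings at the two higher means, 9.5 to 22 times the joint count. At 130/80 it is about 30 readings, roughly 70 to 130 times the joint count. Between 88% and 94% of the diastolic-only additions lie at 100–109.

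**The case against.** The strongest reply is that little is actually missed. Section 22.2 defines an AE broadly, and 22.4 requires recording whatever the severity or relationship to treatment. The 19.6 sentence does not say that other readings are not AEs. A severe elevation that leads to hospitalization or is an important medical event is an SAE, with 24-hour reporting, and 27.2 has the medical monitor review the data for safety. Drug can still be stopped under the last bullet of 16.3.1 or under 23.1. All of that stands, and it keeps the point minor. It does not supply a blood-pressure prompt for isolated rises, and it does not change closure, because SAEs end at the same resolved, stabilized or referred point.

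A second reply is that the 22.5 wording is deliberate, since it repeats the accelerated-hypertension definition in 16.3.1. That is plausible and cannot be excluded. It does not explain the 150/90 wording in 19.6. The purposes also differ: 16.3.1 stops drug for hypertension that cannot be managed, while an AESI directs surveillance.

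A third reply is that widening the AESI would swamp it with moderate readings taken once. This stands against a diastolic-only limb at 100, as Step 4 shows. It does not stand against a systolic-only limb.

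A reader might also infer that the trial will produce no threshold counts by arm. The visible vital-signs analysis in 21.8.3 is descriptive by visit and states none. But neighbouring text is redacted and 21.6 refers to a statistical analysis plan, so their absence cannot be established.

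**Conclusion.** The point holds as a minor wording gap. As written, an isolated severe elevation triggers neither the 19.6 prompt nor the 22.5 AESI, and an AE recorded for it may be closed earlier than an AESI could be. That follows from the text and needs no assumption.

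The size does rest on assumptions. With the distributions above, 10 to 42 of 1,296 readings fall outside both rules, but readings of the 210/88 type make up only 0.01 to 2.9 of them. The rest are diastolic elevations with systolic at or below 150.

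Two stronger readings are not supported. A reader might infer that such events go unrecorded or leave the subject on drug unchecked; 19.3, 22.2, 22.4, 16.3.1 and 23.1 say otherwise. A reader might also infer that 22.5 should become a full either-limit definition. The documents give no basis for a diastolic-only cut-off, and at 100 the category would grow many-fold. The visible text attaches no expedited reporting or separate analysis to AESI status, and the primary endpoint is not affected.

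**What to change.** - **19.6, on-study sentence:** change to systolic >150 and/or diastolic >90, and keep the investigator's judgement of clinical significance. This matches inclusion criterion 10, which limits each pressure separately.
- **22.5:** keep the joint definition and add systolic ≥180 alone as a qualifying limb. Ask the medical team whether a diastolic-only limb is wanted and at what cut-off.
- **Reporting:** tabulate systolic-only, diastolic-only and joint exceedances by arm, unless the redacted text already does so.
- **16.3.1:** leave unchanged.

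The cost is two rewordings, one question to the medical team and three table rows from vital signs already collected. Under the assumed distributions, about 175 to 377 more of 1,296 readings would be put to clinical judgement under 19.6, and fewer than 10 readings would be added to the AESI. Many of these would rest on single measurements. Section 22.5 would no longer mirror 16.3.1. If the joint wording is intended, the sponsor can say so in the text instead.
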